### **4.3 Interim analyses and data monitoring**

Main focus of this interim analysis will be the efficacy and safety up to Week 48. An interim freeze of the database will be performed once all subjects have completed Week 48 of Part A. Part A data will be reported in corresponding Part A tables and listings. All blinded data will remain blinded. In the disposition tables, treatment will remain blinded and be presented according to a dummy treatment assignment for Part B. For the listing only open-label data from Part A will be included. The purpose of the interim analysis is to check whether the assumptions on efficacy of CZP made for the protocol were correct, and to potentially present the results at scientific meetings. No CSR will be written. The following assessments will not be included in the Interim Analysis:

- MRI Efficacy scores (SPARCC (Sacroiliac joint), Spine ASspiMRI-a in Berlin Modification score)
- Work Productivity Questionnaire
- EQ-5D-3L
- Fecal and serum calprotectin
- Correlation between calprotectin and IBD, CRP
- SF36 (domains, PCS, MCS)
- Resource utilization
- PK
- ADAb

The scope of the Interim Analysis will not be covered in a separate Analysis Plan.

No specific data monitoring, steering, or evaluation committee is planned for this study.

The following variable will be classed as unblinding during the full study. Therefore, these variables will be kept blinded until study unblinding after database lock:

- Randomized treatment group
- CRP (Post Week 48)
- MRI Efficacy scores (Post Week 48)
- PK and ADAb (Post Week 48).

#### **4.4 Multicenter studies**

Individual center results will not be directly presented, however as discussed in Section 4.1 geographical region is used as a covariate and some outputs will be presented by geographical region. Centers will be grouped in the following regions: North America, Western Europe, Eastern Europe and Asia.

#### **4.5 Multiple comparisons/multiplicity**

The statistical analysis of the primary efficacy variable will account for the testing of multiple doses by using a fixed sequence testing procedure. The proportion of subjects who do not experience a flare will be compared between each CZP dose and PBO. The predefined order of hypotheses testing, each at a 2-sided 0.05 significance level for the comparison between the given CZP dose and PBO, will be performed in the sequence shown below:

1. CZP 200mg Q2W vs PBO
2. CZP 200mg Q4W vs PBO

The second test will be performed irrespective of whether the first test is significant at the 0.05 level or not. However, the second test will be interpreted as statistically significant only if the first test is significant at the 0.05 level as well.

No adjustment for multiplicity will be considered when analysing the secondary efficacy variables. The p-values calculated in conjunction with those variables will be considered as nominal.

#### **4.6 Use of an efficacy subset of subjects**

The primary efficacy analysis from Part B will be repeated using the FAS and the PPS as a supportive analysis.

#### **4.7 Examination of subgroups**

The primary efficacy variable and PK variables will be summarized using the following subgroups:

- mNY classification (mNY positive, mNY negative)
- Geographical region (North America, Western Europe, Eastern Europe and Asia)
- Age (<30 and  $\geq$ 30 years)
- Gender

- Race (white and non-white)
- Baseline CRP level ( $\leq$ upper limit of normal (ULN),  $>$ ULN)
- ADAb status (Negative, Positive  $<$ 512, Positive 512- $<$ 1024, Positive  $\geq$ 1024).

These analyses will be based on descriptive statistics only.

## **5 STUDY POPULATION CHARACTERISTICS**

### **5.1 Subject disposition**

The number and percentage of subjects who entered the study, completed Part A, discontinued from Part A with reasons for discontinuation, were randomized into Part B, completed Part B (without flare, after flare) and discontinued Part B as well as started Escape Part, completed Escape Part and discontinued Escape Part with reasons for discontinuation will be presented.

Subjects who completed Week 48 without SFU are considered as completed Part A. Subjects completed Week 96 in Part B or in Escape Part without SFU visit are considered as completed Part B or completed Escape Part, respectively.

Subjects are considered to have started Escape Part, if they experienced a flare and have been moved to escape treatment via IXRS system (even if they do not receive any escape treatment).

This summary will be based on the ES and will present subjects overall and broken out by axSpA subpopulation.

Discontinuations due to AEs will also be presented. This summary will be based on the ES and will present subjects overall and broken out by axSpA subpopulation.

The disposition of subjects screened by geographical region and overall, including the number of subjects in each analysis set will be summarized. This summary will be based on the ES and will present subjects overall (ie not broken out by axSpA subpopulation).

A summary table of reasons for screen failures will be provided.

The following listings will be produced based on the ES:

- A listing of subject analysis sets
- A listing of subjects who did not meet study eligibility criteria
- A listing of subject disposition

The following listings will be produced based on the OLS:

- A listing of study discontinuation
- A listing of visit dates
- A listing of important protocol deviations (including any reasons for exclusion from the PPS)

### **5.2 Protocol deviations**

Important protocol deviations that are likely to have an impact on the subject's rights, safety, well-being, and/or on the validity of the data for analysis will be identified during the blinded data evaluation meeting.

The identified important protocol deviations will be classified by pre-specified items (e.g., informed consent, inclusion and exclusion criteria, IP administration/study treatment, withdrawal criteria, disallowed medications, procedures/tests, visit schedule, safety and other) as well as study period of occurrence (Part A, Part B) and summarized in Part A using the OLS, in Part B using the RS and overall using the OLS.

All important protocol deviations will be provided in a data listing using the OLS.

## **6 DEMOGRAPHICS AND OTHER BASELINE CHARACTERISTICS**

### **6.1 Demographics**

The following demographic variables will be summarized by axSpA subpopulation and for all subjects combined using the OLS. This presentation will also be produced for the RS by treatment group.

Continuous variables: age (years), height (cm), weight (kg) and body mass index (BMI; kg/m^2)

Categorical variables: age (<30 years,  $\geq$ 30 years and also  $\leq$ 18, 19 to 24, 25 to 34, 35 to 44,  $\geq$ 45), gender (male, female), racial group (American Indian/Alaskan Native, Asian, Black, Native Hawaiian or Other Pacific Islander, White, Other/Mixed), ethnicity (Hispanic or Latino, Not Hispanic or Latino), BMI category (<18.5, 18.5 - <25, 25 - <30, 30 - <35, 35 - <40,  $\geq$ 40) and region and country as per [Table 3.4](#) .

All demographic details will be listed using the OLS.

### **6.2 Other Baseline characteristics**

Lifestyle (alcohol, caffeinated beverages) and Tobacco usage at Baseline will be summarized by axSpA subpopulation and for all subjects combined using the OLS.

The responses to the 4 criteria for Modified NY Criteria for AS will be summarized by axSpA subpopulation and for all subjects combined in frequency tables using the OLS. This table will be also produced for the RS by treatment group.

Similarly, the responses to the following modified ASAS classification criteria for AS will be summarized by axSpA subpopulation and for all subjects combined in frequency tables using the OLS. This table will be also produced for the RS by treatment group.

- back pain of  $\geq$ 3 months and subject's age at onset <45 years
- inflammatory back pain
- arthritis
- enthesitis
- uveitis
- dactylitis
- psoriasis
- Crohn's disease (CD)/ulcerative colitis

- HLA-B27
- elevated CRP
- presence of sacroiliitis on imaging including imaging method

History of extra-articular manifestations will be summarized by axSpA subpopulation and overall in frequency tables using the OLS. This table will be also produced for the RS by treatment group.

- History of uveitis
- History of IBD
- History of psoriasis

Frequency tables by axSpA subpopulation and overall using the OLS will also be provided for:

- History of latent tuberculosis
- Tuberculosis test
- Chest x-ray
- Sacroiliac joint x-ray

All baseline characteristics described above as well as baseline extra-articular manifestations will be listed using the OLS.

For subjects randomized to Part B, frequency tables by treatment group using the RS and overall will be provided for the randomization stratification factors:

- Geographic region
- mNY classification

Summaries of the randomization stratification factors will include both the original values of the stratification factors (ie, as used for randomization) as recorded in the IXRS and the final values of the stratification factors (ie, updated values in case any modifications were made after randomization). The randomization stratification factors will also be listed using the RS.

### **6.3 Medical history and concomitant diseases**

Previous and ongoing medical history will be summarized by MedDRA® system organ class (SOC) and preferred term (PT).

Previous and ongoing medical history will be summarized by axSpA subpopulation and for all subjects combined in Part A using the SS, by treatment group and for all subjects combined in Part B using the SSB, and will be listed using the SS.

Time since diagnosis of disease and symptom duration will be summarized by axSpA subpopulation and for all subjects combined in Part A using the OLS, by treatment group and for all subjects combined in Part B using the RS. Time since diagnosis will also be categorized into  $\leq 2$  and  $>2$  years, and symptom duration will be categorized into  $\leq 3$  and  $>3$  years.

Time since diagnosis of disease will be defined as: Date of first study medication administration minus earliest start date of the medical history of any of the preferred terms 'Axial Spondyloarthritis', 'Spondyloarthropathy', 'Ankylosing spondylitis', or 'Spondylitis'. If a subject

does not have a history of any of the above 4 preferred terms, then the time since diagnosis of disease will be set equal to the symptom duration.

Symptom duration will be calculated as:

$$(\text{Date of first study medication administration} - \text{Start date of symptoms})/365.25$$

The start date of symptoms will be found using the medical history of the subject using the following rules (including imputation of partial dates as described for concomitant medications in Section 4.2):

- Subjects with a medical history preferred term of 'Back pain', 'Inflammatory pain', 'Spinal Pain', 'Lumbar spine pain' and a start date present will use the earliest start date of these symptoms as the start date of symptoms.
- Otherwise, subjects with a preferred term of 'Axial spondyloarthritis', 'Spondyloarthropathy', 'Ankylosing spondylitis', or 'Spondylitis' will use the earliest start date of disease as the start date of symptoms
- Otherwise, the subject's medical history will be reviewed in the DEM meeting to determine if the subject has evidence of a start date of symptoms or primary disease.
- If the resulting symptom duration is unknown or is below 3 months, the imputed start date will be set to 3 months and 1 day prior to the start of treatment so that the symptom duration is imputed as 3 months.

Time since diagnosis and symptom duration as described above will be listed using the OLS.

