- If start day is missing, but month and year are present, start date will be replaced by the first day of the month of that year or by the day of start of study medication in Part A, if study medication in Part A was first administered in that month and year (exception: if in this case start date is after stop date, also the first day of the month will be utilized).
- If start day and month is missing for one item diagnosis (medical history of any of the preferred terms 'Axial Spondyloarthritis', 'Spondyloarthropathy', 'Ankylosing spondylitis' , or 'Spondylitis') or symptom (medical history preferred term of 'Back pain', 'Inflammatory pain', 'Spinal Pain', 'Lumbar spine pain') and the year is similar, the missing month will be imputed by the month of the other item.
- If only one item diagnosis or symptom is present and if start day and month are missing and year is present, start date will be replaced by the first of January of that year or by the day and month of start of study medication in Part A, if study medication in Part A was first administered in that year (exception: if in this case start date is after stop date, also the first day of January will be utilized).
- If start day, month, and year are missing, start date will be replaced by the date of first study drug administration in Part A or by the first day of January of the year of the end date, if the first administration date is after the end date.

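### Baseline disease duration: symptom onset can fall after diagnosis, and a wholly undated diagnosis is counted as made on the first-dose day

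*SAP*

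**What the plan says.** Section 6.3 defines two baseline durations.

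- **Symptom duration** is first dose minus start of symptoms, divided by 365.25. Start of symptoms follows a hierarchy. A subject with one of four pain terms "and a start date present will use the earliest start date of these symptoms as the start date of symptoms". Failing that, a subject with one of four disease terms "will use the earliest start date of disease as the start date of symptoms". Failing that, the history is reviewed at the data evaluation meeting. A last rule, which begins "If the resulting symptom duration is unknown or is below 3 months", resets the value to 3 months.
- **Time since diagnosis** is "Date of first study medication administration minus earliest start date of the medical history of any of the preferred terms" for the disease. It has no lower limit. Only a subject with none of the four disease terms is given the symptom duration instead.

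Both durations are summarized by axSpA subpopulation for the Open-Label Set and by treatment group for the Randomized Set, with cuts at 2 years (diagnosis) and 3 years (symptoms), and are listed by subject.

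The medical-history part of section 4.2 states: "If start day, month, and year are missing, start date will be replaced by the date of first study drug administration in Part A". If first dose is after the end date, 1 January of the end-date year is used instead. Where only one diagnosis or symptom item exists and only its year is known, the date becomes 1 January or is completed "by the day and month of start of study medication in Part A, if study medication in Part A was first administered in that year". Where the other item falls in a similar year, its month is borrowed.

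For symptom onset, however, 6.3 works from its own pointer: "including imputation of partial dates as described for concomitant medications in Section 4.2".

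**The concern.** Symptoms of axial spondyloarthritis should not be tabulated as starting years after the diagnosis. Back pain is a generic term, and one later-dated entry overrides a known earlier diagnosis.

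The first-dose default for an unknown date has the same wording as the adverse-event rule in 4.2. There, assuming onset on treatment is the cautious choice. A diagnosis precedes treatment, so for it the first-dose day is the latest date possible. An unknown value then enters the table as an observed 0.

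At stake is the description of how early in their disease the subjects are, above all the counts either side of the 2-year and 3-year cuts. The outdated pointer adds a smaller risk: two programmers could derive different onset dates from the same record.

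**Working it through.** **The plan's own figure.** Setting onset 3 months and 1 day before first dose gives 90 to 93 days, depending on the calendar. Divided by 365.25 this is 0.246 to 0.255 years, or 2.96 to 3.06 months, which agrees with the stated 3 months.

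**Invented subjects, first dose 1 September 2015.** The SAP gives no subject data, so these only show how the rules behave. Durations are days / 365.25.

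| Subject | Diagnosis date | Pain entry | Time since diagnosis | Symptom duration |
|---|---|---|---|---|
| A | 1 Jan 2008 | 1 Mar 2015 | 2800 / 365.25 = 7.7 y (>2) | 184 / 365.25 = 0.5 y (≤3) |
| B | fully missing, ongoing | 1 Sep 2005 | 0 (≤2) | 3652 / 365.25 = 10.0 y (>3) |
| C | fully missing, ongoing | none | 0 (≤2) | reset: 93 / 365.25 = 0.25 y (≤3) |
| D | year 2015 only | none | 0 (≤2) | reset: 0.25 y (≤3) |

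- **A:** the first rule of the hierarchy applies, so the 2008 date is never consulted. Symptoms start 7.7 − 0.5 = 7.2 years after diagnosis. Using the earliest of all eight terms gives 7.7 years, which moves A to the category above 3 years.
- **B:** the undated diagnosis is set to first dose, giving 0. Symptom duration is unaffected because a dated pain entry exists.
- **C:** the imputed diagnosis date also serves as symptom onset, which is below 3 months and is reset. Because a disease term is present, the review at the data evaluation meeting is bypassed.
- **D:** the true diagnosis date lies between 1 January and 1 September 2015, so true time since diagnosis is at most 243 / 365.25 = 0.67 years. The 0 is inexact, but the category of 2 years or less is correct.

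**Cross-reference.** Take a pain entry known only as 2010 and a diagnosis in September 2010. The medical-history rules borrow September; with the first of the month for the missing day, onset is 1 September 2010. The medication rules give 1 January 2010. The results differ by 243 / 365.25 = 0.67 years. For a missing day alone, and for a fully missing date, the two sets agree. The amendment log explains the mismatch: Amendment 1 wrote the pointer, and Amendment 2 added the medical-history rules.

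**The case against.** The strongest defence is that the effect is small. Neither duration is a stratification factor, a term in the primary logistic model or one of the subgroups in section 4.7. Both are listed by subject, so an onset later than diagnosis would be seen. Taking pain terms first is a sensible order if sites recorded disease-related onset there. The number of subjects affected cannot be known from the SAP. All of this stands. It limits the weight of the point but does not make the derived values right.

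A reader might also infer more than the text supports:

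- *That symptom duration can be zero.* It cannot, because the 3-month reset prevents it.
- *That every undated diagnosis forces symptom duration to 3 months.* It does so only where no dated pain entry exists (C, not B). The reset is also in line with the classification item in 6.2 that requires at least 3 months of back pain.
- *That year-only dates in the first-dose year move subjects across a cut.* For time since diagnosis they do not, as D shows.
- *That first dose replaces every unknown date.* An earlier end date, or a second item in a similar year, changes the imputed date.
- *That all imputation shortens duration.* Partial dates outside the first-dose month or year go to the first of the month or 1 January, which tends to lengthen it.
- *That undated pain entries are mishandled.* The first rule requires a start date, so they fall through to the disease date.

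**Conclusion.** The point holds in a narrow form. Two rules produce wrong baseline values: a symptom hierarchy that ignores an earlier diagnosis, and a first-dose default for a diagnosis date that is missing in full with no earlier end date. The first can understate symptom duration by years (7.7 reduced to 0.5 in the example). The second records 0 for an unknown time since diagnosis and places it at or below the 2-year cut. Where there is also no dated pain term, symptom duration is set to 3 months. The pointer in 6.3 is out of date and matters only for year-only dates.

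The reach is descriptive: baseline tables for the Open-Label Set, by-arm tables for the Randomized Set, and listings. The primary analysis is untouched, and nothing in the SAP suggests a difference between arms. The reading of the rules is firm; the number of subjects affected is unknown and depends on how sites recorded medical history. This is a minor correction.

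**What to change.** 1. In 6.3, define start of symptoms as the earliest available date among the four pain and four disease preferred terms. Send subjects with no date under any of the eight to the review that 6.3 already provides.
2. In 4.2, leave a diagnosis date that is missing in full as missing. Show the number missing in the time-since-diagnosis table. Keep the substitution of symptom duration for subjects who have no disease term at all.
3. In 6.3, refer to the medical-history date rules of 4.2 instead of the medication rules.

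The year-only rule can stay, since it does not change the time-since-diagnosis category.

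The cost is a few lines of SAP text and a small change to one derivation. The one visible downside is a possible missing row in the baseline table.

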#### **6.4 Past, prior and concomitant medications**

Past medication summaries will be generated for disease-modifying antirheumatic drugs (DMARDs), non-steroidal anti-inflammatory drugs (NSAIDs), and anti-tumor necrosis factors (anti-TNFs) by anatomical therapeutic chemical (ATC) code (level 3 (4-digit) decode, level 4 (5-digit) decode, and PT). See Section 3.2.29 for definition of past, prior and concomitant medications.

For Part A, prior DMARDs and NSAIDs will be summarized by WHO-DD ATC code (level 3 (4-digit) decode, level 4 (5-digit) decode, and PT). No extra table for prior anti-TNFs will be produced due to the fact that this summary is identical to the 1 for the past anti-TNFs.

Summaries will be presented by axSpA subpopulation and overall using the SS.

For Part A, prior medications (except DMARDs and NSAIDs) will be summarized by WHO-DD ATC code (level 2 (3-digit) and level 3 (4-digit) decode. Summary will be presented by axSpA subpopulation and overall using the SS.

For Part A, concomitant DMARDs and NSAIDs will be summarized by WHO-DD ATC code (level 3 (4-digit) decode, level 4 (5-digit) decode, and PT). Summaries will be presented by axSpA subpopulation and overall using the SS.

For Part A, concomitant medication (except DMARDs and NSAIDs) will be summarized by WHO-DD ATC code (level 2 (3-digit) and level 3 (4-digit) decode. Summary will be presented by axSpA subpopulation and overall using the SS.

For Part B, prior DMARDs and NSAIDs will be summarized by WHO-DD ATC code (level 3 (4-digit) decode, level 4 (5-digit) decode, and PT). Summaries will be presented by treatment group and overall using the SSB.

For Part B, prior medications (except DMARDs and NSAIDs) will be summarized by WHO-DD ATC code (level 2 (3-digit) and level 3 (4-digit) decode. Summary will be presented by treatment group and overall using the SSB.

For Part B, concomitant DMARDs and NSAIDs will be summarized by WHO-DD ATC code (level 3 (4-digit) decode, level 4 (5-digit) decode, and PT). Summaries will be presented by treatment group and overall using the SSB. Additionally, in subjects experiencing a flare in Part B, separate summaries by treatment group using the ETS will be provided presenting pre-flare and post-flare concomitant medications.

For Part B, concomitant medications (except DMARDs and NSAIDs) will be summarized by WHO-DD ATC code (level 2 (3-digit) and level 3 (4-digit) decode. Summary will be presented by treatment group and overall using the SSB. Additionally, in subjects experiencing a flare in Part B, separate summaries by treatment group using the ETS will be provided presenting pre-flare and post-flare concomitant medications.

Prohibited medication use and date of first usage will be determined and documented during the pre-analysis review meeting prior to the database lock.

The number and percentage of subjects who used prohibited medication will be summarized by axSpA subpopulation and overall in Part A using the SS and by treatment group and overall in Part B using the SSB. Separate summaries in subjects experiencing a flare in Part B by treatment group using the FS will be provided presenting pre-flare and post-flare prohibited medication. An overall summary of subjects who used prohibited medication in Part A or Part B will be provided using the SS.

Prohibited medications will be assigned to Part A or Part B (overall, pre-flare, post-flare) using the same rules as outlined for concomitant medications in Section 3.2.29 .

Prior and concomitant medications and prohibited medications will be listed using the SS.

